## **Aim**

The overall aim of the study is to investigate whether patients with Alzheimer's disease and patients with Lewy body dementia have a higher incidence of subclinical epilepsy as compared with healthy elderly controls and whether subclinical epilepsy is correlated with blood flow in the brain as measured with MRI.

Objective 1: Investigate whether it is possible to use ear EEG for long-term monitoring of patients with Alzheimer's disease (feasibility and compliance)

Hypothesis: Ear-EEG monitoring is possible in patients with Alzheimer's disease.

Objective 2: Investigate the incidence of paroxysmal activity in patients with Alzheimer's disease and Lewy Body dementia as measured by ear EEG as compared to healthy elderly controls

The study is considered exploratory as recordings with ear EEG and also long-term EEG recordings have never carried out in this patient group before.

Objective 3: Investigate the regional blood flow (rCBF) measured by MRI in the hippocampus in patients with Alzheimer's disease.

Hypothesis: Patients with Alzheimer's disease will have an increased rCBF in the hippocampus compared to healthy controls.

Objective 4: Investigate the correlation between increased blood flow in the hippocampus and paroxysmal activity measured by the ear EEG.

Hypothesis: Increased rCBF in the hippocampus in patients with Alzheimer's disease is associated with paroxysmal activity measured by ear EEG.

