## **Study Design**

The project consists of two sub-studies:

1) Feasibility study (Aim 1)

2) The main study (Aim 2-4)

Both sub-studies are longitudinal studies with 3 periods of 2 days of ear-EEG recordings in the patients' homes over 6 months. The healthy controls will undergo ear-EEG recording once. All participants must have had an MRI of the brain at the beginning of the study.

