### **The main study**

In the main study, we will include an additional 40 patients with Alzheimer's disease and 50 healthy control subjects as well as 20 patients with Lewy body dementia. The patients with Alzheimer's disease and Lewy body dementia will undergo the same program as for the pilot project but the total time of ear-EEG recording may be extended to up to five days.

The healthy subjects will first be examined by a physician including cognitive tests and a questionnaire on everyday activity of daily living from any relatives will be performed. On

subsequent visits, participants will undergo an MRI scan as well as a conventional EEG examination and wear the ear-EEG device for a total of 48 hours. The inclusion of healthy subjects is done in order to compare ear-EEG, conventional EEG and MRI scans in patients with AD and DLB with healthy elderly persons.

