### **Statistical analysis plan**

The study is considered exploratory since recordings with ear EEG have never been performed and only one other study has looked at long-term EEG recordings.

For the feasibility study, we plan to review the EEGs together with the feedback we receive from the participants to investigate whether they were able to wear the ear-EEG at least 24 hours in 2 days, and that over 50% were able to record at least 5 hours of sleep.

If we continue with the main study, we will investigate how frequent we observed paroxysmal activity as measured on the ear-EEG in patients with Alzheimer's disease and Lewy body dementia as compared to healthy elderly controls. Furthermore, we will compare the frequency of paroxysmal activity and CBF in the hippocampus as measured with ASL-MRI.

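### Does the blood-flow analysis need correcting because the SAP names no population for it and has no sentence for the AD v control comparison?

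*Combined protocol and SAP*

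**What the plan says.** The combined protocol and SAP mentions blood flow in four places.

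- **Aim, overall aim.** One sentence asks two things. The first is whether "patients with Alzheimer's disease and patients with Lewy body dementia have a higher incidence of subclinical epilepsy as compared with healthy elderly controls". The second is "whether subclinical epilepsy is correlated with blood flow in the brain as measured with MRI". The groups are named in the first clause only.
- **Aim, Objectives 3 and 4.** The Objective 3 hypothesis is "Patients with Alzheimer's disease will have an increased rCBF in the hippocampus compared to healthy controls". The statement of Objective 4 names no population, but its hypothesis does: "Increased rCBF in the hippocampus in patients with Alzheimer's disease is associated with paroxysmal activity measured by ear EEG".
- **The main study.** Enrolling controls "is done in order to compare ear-EEG, conventional EEG and MRI scans in patients with AD and DLB with healthy elderly persons", so a comparison of MRI is foreseen.
- **Statistical analysis plan.** After a sentence comparing paroxysmal activity in AD and Lewy body dementia with controls, it adds that "we will compare the frequency of paroxysmal activity and CBF in the hippocampus as measured with ASL-MRI".

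On numbers, the Feasibility study section recruits 10 AD patients. The main study section says "we will include an additional 40 patients" with AD, together with 50 controls and 20 patients with Lewy body dementia. Study Design assigns Aims 2 to 4 to the main study.

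**The concern.** Read alone, the SAP sentence on blood flow could be applied to AD patients only (40 or 50), to AD and Lewy body dementia (60 or 70), or to everyone (110 or 120). These are different questions. The protocol expects higher hippocampal blood flow in AD than in controls, and it asks whether paroxysmal activity is also more common in AD. If both are true, a correlation across all participants with no term for group is partly the group difference in disguise. It could suggest a link that does not exist among AD patients, or hide one that does if blood flow turned out lower in AD.

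Two smaller points come with this. Objective 3 carries a directional hypothesis but has no sentence of its own in the SAP. It is also not stated whether the 10 feasibility patients count towards Objectives 2 to 4.

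**Working it through.** The plan states no alpha, power or effect size, so there is no figure of its own to reproduce. The check is first textual, then numerical.

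**1. Is there a contradiction over the population?**

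| Place | Population named for the correlation |
|---|---|
| Overall aim, correlation clause | none |
| Objective 4, statement | none |
| Objective 4, hypothesis | AD |
| SAP sentence on blood flow | none |

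One population is stated and three places are silent. Taking the overall aim to mean all groups is an inference from a clause without a limit; AD plus Lewy body dementia would fit it as well. The specific hypothesis is the natural guide.

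**2. Is Objective 3 missing?** The Aim section gives the measure, region, groups and direction, and the main study section gives comparison of MRI scans as a reason for enrolling controls. The SAP sentence could also be read as comparing both measures between groups, which would cover Objective 3 and leave Objective 4 without a sentence. On either reading the Aim section supplies what is left out.

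**3. How many AD patients?** 10 + 40 = 50, the same as the number of controls, and main-study patients follow the programme of the pilot. The word additional points to 50, although no sentence says so.

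**4. What would unadjusted pooling cost?** Inputs: 50 AD and 50 controls; activity in 42.2% and 10.5% (Background; the first is an upper figure and neither is from ear-EEG). Assumed: a blood-flow difference of *d* SD, two-sided 5%, and no link within either group. With equal groups and mean activity p = (0.422 + 0.105)/2 = 0.2635, the expected pooled correlation is

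r = 0.25·d·(0.422 − 0.105) / √[p(1 − p)(1 + 0.25·d²)]

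At d = 0.5: 0.25 × 0.5 × 0.317 = 0.0396; p(1 − p) = 0.1941; √(0.1941 × 1.0625) = 0.4541; r = 0.0396/0.4541 = 0.087.

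| d (SD) | Expected pooled r | Pooled rejection (20,000 simulated trials) |
|---|---|---|
| 0 | 0 | 5.2% |
| 0.3 | 0.053 | 8.4% |
| 0.5 | 0.087 | 14.0% |
| 0.8 | 0.134 | 26.7% |

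A second simulation, using event frequency and a rank correlation with 40 or 50 AD patients, gives 8.0–8.5%, 13.5–14.5% and 25.8–26.9% at the same three differences. Analysed within AD, or with a group term, rejection stays at 4.6–5.7%.

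**5. What can the AD-only analysis detect?** By Fisher's z, the detectable r at 80% power and two-sided 5% is tanh[(1.960 + 0.842)/√(n − 3)]:

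- n = 40: tanh(2.802/6.083) = 0.43
- n = 50: tanh(2.802/6.856) = 0.39

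For Objective 3, the 95% CI half-width is t·√(1/n₁ + 1/n₂) SD:

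- 40 v 50: 1.987 × 0.2121 = 0.42 SD
- 50 v 50: 1.984 × 0.2 = 0.40 SD

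Settling whether there are 40 or 50 AD patients therefore changes precision only slightly.

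**The case for a change.** The strongest case for a change is that calling a study exploratory excuses the lack of a power calculation, but does not tell a reader whose correlation will be reported. Objectives 3 and 4 carry explicit hypotheses, the SAP sentence follows a three-group sentence, and the remedy would be about three sentences with no added visit or measurement. All of that is fair. It is true that the SAP section names no population and has no explicit sentence for Objective 3.

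The argument from harm is weaker. The inflation arises only if groups are pooled without a group term, which no passage proposes. The most striking contrast depends on direction. Suppose there is a real link in AD (mean rank correlation 0.33). Power is then 10–14% pooled against 57–68% within AD, but only if AD blood flow is 0.5 SD *lower* than in controls, the opposite of the Objective 3 hypothesis. With AD 0.5 SD *higher*, pooled rejection is about 68% (40 AD) to 79% (50 AD), against 58% and 68% within AD. At 0.3 SD higher the two are about equal. Part of the pooled figure at 0.5 SD is the group difference itself, so this is no argument for pooling. It shows that the loss is not the expected case.

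**Conclusion.** No change follows. The documents do not give two conflicting populations: the Objective 4 hypothesis says AD, and the other places are silent. An analyst who takes the hypothesis as the guide, makes the Objective 3 contrast described in the Aim and main study sections, and counts 10 + 40 = 50 AD patients would reach sound results. Writing this into the SAP would be a useful clarification, but it would record what is already intended without correcting a stated rule, number or method.

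The size of the risk is conditional. Rejection of about 8% to 27% in place of 5% requires an unadjusted pooled correlation, an assumed blood-flow difference of 0.3 to 0.8 SD, an assumed 5% level, and activity rates from other recording methods. At 0.5 SD the expected spurious correlation is about 0.09, which is small in a study that describes itself as exploratory and sets no significance threshold. The conclusion would differ if the documents proposed a pooled correlation without a group term as the test of Objective 4.
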